### 7.6.2 Anesthesia

The surgery will be performed under general endotracheal anesthesia. Epidural or spinal analgesia, regional nerve blocks, intra-abdominal application of local anesthetics, and peri-incisional injection of local anesthetics other than the test drug have been prohibited. Intra-operative opioid analgesia will be limited to IV fentanyl with a maximum dose of 2.5 mcg/kg/hr, including the induction dose. The duration of the surgical procedure is anticipated to be approximately 1 hour. See [Section 5.5 Anesthesia Requirements](#) for additional details.

### 7.6.3 Rescue Analgesia for Postoperative Pain Management

#### PACU

- IV fentanyl 12.5 or 25 mcg bolus doses given at no less than 5-minute intervals

#### Home Use

- Oxycodone IR 5 mg tablets
- Acetaminophen 500 mg tablets

#### 7.6.3.1 PACU Rescue Medication Regimen

In the PACU, pain may be treated with rescue analgesia (IV fentanyl in 12.5 or 25 mcg doses given at no less than 5-minute intervals). IV fentanyl should be given only as necessary to control pain, only at the patient’s request, and not as a scheduled or prophylactic dose. The patient’s pain score CC on movement (defined as sitting up, or attempting to do so, from a supine position) should be assessed immediately before giving each rescue dose of IV fentanyl. If the patient is unable to sit up completely due to severe pain, weakness, or lack of recovery from anesthesia, the patient should be instructed to make his or her best attempt, and that score will be recorded. The dose and time of administration of IV fentanyl and associated pain scores

must be recorded on the patient's chart and on the eCRF. No IV acetaminophen, IV NSAIDs, or any analgesic drug (including Toradol® [ketorolac] Injection, Caldolor® [ibuprofen] Injection, and Ofirmev® [acetaminophen] Injection) other than IV fentanyl should be given during the PACU stay. However, the following exception will apply: at sites where patients are transferred prior to discharge to a Phase 2 recovery unit (or step down unit), then oral oxycodone or oral acetaminophen may be given according to the instructions described in Section 7.6.3.2 for the use of oral rescue medication.

#### 7.6.3.2 Oral Rescue Medication Regimen for Home Use

**Patients will be provided written instructions regarding rescue medication usage prior to discharge. Prior to rescue dosing, the patient must record pain intensity CCI on movement. Each dose of rescue medication will be recorded by the patient on the LogPad.**

**From PACU discharge through Study Day 8 (POD 7), analgesic rescue medications have been limited to oxycodone IR 5 mg tablets, prescribed by the surgeon (or surgeon's DEA licensed delegate), and acetaminophen 500 mg tablets, supplied by the Sponsor.**

**Patients must be instructed to not take both oxycodone and acetaminophen within 4 hours of each other.** Generally, oxycodone should be taken for moderate to severe pain and acetaminophen should be taken for mild to moderate pain and the two drugs should not be taken together.

No Combination products (e.g., Percocet, Vicodin, Vicoprofen, Zydone, Percodan) or extended release opioid products (e.g., Oxycontin, Opana ER, Kadian, Ultram ER) will be permitted from screening to trial completion (Study Day 60).

Patients will be instructed that they must bring any unused rescue medication (oxycodone IR and acetaminophen) with them to the clinic visits (through Visit 6 or early termination) for reconciliation purposes. The number of tablets dispensed will be recorded and the number of remaining tablets will be counted at each clinic visit.

##### 7.6.3.2.1 Rescue Oral Opioid

For the treatment of moderate to severe pain, patients will be prescribed oxycodone IR 5 mg tablets. Exactly 24 tablets should be prescribed. One or two tablets may be taken every 4 hours for moderate to severe pain. Each dose of oxycodone will be recorded by the patient on their LogPad.

##### 7.6.3.2.2 Rescue Oral Acetaminophen

For the treatment of mild to moderate pain, patients will be supplied by the sponsor with acetaminophen 500 mg tablets (one bottle of 24 tablets). One or two tablets may be taken every 4 hours as required for pain. **No more than 8 tablets (4000 mg) may be taken in any 24 hour period.** Each dose of acetaminophen will be recorded by the patient on their LogPad. A screen

will display an alert that they have reached the maximum allowed dose when a patient takes an 8th tablet (4000 mg total) in any 24 hour period.

#### 7.6.3.2.3 No Concomitant Use of Oxycodone and Acetaminophen

Oxycodone and acetaminophen may not be taken concomitantly within the same four hour interval.

#### 7.6.3.3 Recording of Rescue Analgesia Data

Identity, dose and time of administration of rescue analgesia, will be recorded as follows:

- IV rescue medication and associated pre-rescue pain scores CCI on movement – On the appropriate source document and eCRF from patient awakening from anesthesia to discharge.
  - If the patient is unable to sit up all the way due to severe pain, weakness, or lack of recovery from anesthesia, the patient should be instructed to make his or her best attempt, and that score will be recorded (e.g. if patient can only sit up partway, then the pain that the patient feels in that position will be recorded).
- Oral rescue medication (oxycodone or acetaminophen) in the LogPad till Study Day 8 (POD 7) and associated pre-rescue pain scores CCI on movement through Study Day 4 (POD 3).
- Rescue medication including NSAIDs taken for pain relief after Study Day 8 (POD 7) will be recorded on the appropriate source document and CM eCRF.
- The number of oxycodone and acetaminophen tablets prescribed/dispensed and the number of tablets remaining at each clinic visit will be recorded on the appropriate source document and eCRF.

The LogPad will be the primary data source for oral opioid rescue medication taken through Study Day 8 (POD 7) and the eCRF will be the primary data source for IV rescue medication taken throughout the trial and oral rescue medication taken after Study Day 8 (POD 7).

## 8.0 Assessment of Efficacy

### 8.1 Efficacy Assessments

#### Primary Efficacy Endpoint:

- Pain intensity on movement measured at scheduled time points from 0-48 hours following test drug administration, adjusted for prior rescue medication use and analyzed by a mixed effect ANOVA model of repeated measures (MMRM).

To account for the impact of rescue medication use on the scheduled pain scores, the half-life substitution method will be used. Specifically, if the scheduled pain score has been assessed within one plasma half-life after the use of rescue medication (IV or oral opioid or oral acetaminophen), and if the pre-rescue medication pain score is higher than the scheduled one, then the pain score recorded at the time of rescue medication administration will be substituted for the scheduled pain score (FDA, 2014). If a rescue medication pain score is missing, then the worst pain score up to that point will be substituted instead

Key Secondary Efficacy Endpoint:

Pain intensity on movement measured at scheduled time points from 0-72 hours following test drug administration, adjusted for prior rescue medication use and analyzed by a mixed effect ANOVA model of repeated measures (MMRM). Additional Secondary Efficacy Endpoints:

Total IV morphine-equivalent dose of rescue opioids used during 0-72 hours following test drug administration (standard conversion factors are used to convert different opioids to IV morphine-equivalents; CCI [REDACTED])

- Composite endpoint of Silverman’s Integrated Analgesic (SIA) assessment score (Dai et al, 2013 and Silverman et al, 1993) over 0-72 hours following test drug administration
- Proportion of patients taking no opioid rescue medication from PACU discharge until 72 hours after test drug administration
- Time to first opioid rescue medication use after PACU discharge
- Time to PACU discharge eligibility as assessed by mPADSS (Chung, 1995; Awad and Chung, 2006)

CCI [REDACTED]

[REDACTED]

[REDACTED]

[REDACTED]

## 8.2 Method and Rationale for Assessments

### 8.2.1 Pain Intensity Endpoints

Pain intensity evaluations will be completed [CCI] on movement (defined as sitting up, or attempting to do so, from a supine position). [CCI]

[CCI] Patients should then record their pain-on-movement score by sitting up, or attempting to do so, from a supine position and recording the worst pain experienced during the movement.

Patients will assess their pain intensity using an 11-point Numeric Pain Rating Scale (NPRS) (Breivik et al. 2008; Hjermstad et al 2011; Cook et al 2013), [CCI] with numerical rating scale (NRS) scores ranging from 0 (no pain) to 10 (worst pain imaginable). Each patient completes the NPRS by selecting the appropriate score on the scale and recording the score in the LogPad at the scheduled times noted in Table 2: Patient LogPad Schedule of Events and prior to taking an oral rescue medication through Study Day 4 (POD 3). Prior to receiving each dose of IV rescue medication in the PACU, the patient's pain scores [CCI] on movement (defined as sitting up, or attempting to do so, from a supine position) should be assessed and site personnel will record it on the appropriate source document and eCRF.

- If the patient is unable to sit up all the way due to severe pain, weakness, or incomplete recovery from anesthesia, the patient should be instructed to make his or her best attempt, and that score will be recorded (e.g. if patient can only sit up partway, then the pain score that the patient feels in that position will be recorded).
- Patients must **not** use motorized bed or recliner controls to sit up or receive assistance from a caregiver for the pain on movement assessments.
- All patients will watch the training video which is designed to inform the patient of the research goals of the trial, how to properly estimate their pain scores and how to appropriately use rescue medications.

Patient-reported pain is an established variable to capture postoperative analgesic effects (FDA, February 2014).

### 8.2.2 Rescue Opioid Endpoints

Rescue opioid medication (both IV and oral) may be taken for postoperative pain relief and will be recorded as noted in Section 7.6.3.

All opioid doses, whether administered IV or orally, will be converted into IV morphine milligram (mg) equivalents, a standard procedure to allow the calculation of analgesic effects even if opioids of different potency are used [CCI]

Reduction of opioid consumption after surgery is an important potential benefit of SABER®-Bupivacaine. Total opioid use over the first 72 hours following surgery will therefore

be evaluated as a secondary endpoint. The 72-hour assessment period corresponds with the expected duration of SABER®-Bupivacaine activity and the interval during which postoperative pain scores will be assessed. All opioid medications consumed during this period, including those administered intravenously in the PACU and those taken orally by the patient at home will be counted toward the total.

Two other measures of opioid use will also be assessed as secondary endpoints: (1) the time to first use of opioid rescue medication by the patient after discharge from the PACU (oral oxycodone in all cases except possibly those in which the subject has an unplanned admission to the hospital after surgery) and (2) the percentage of patients not requiring any opioid rescue medication after discharge from the PACU until 72 hours after test drug administration. In both these cases, only opioid analgesics administered after PACU discharge will be counted. The rationale for this arrangement is twofold. First, such opioid-sparing effects would likely be more meaningful if demonstrated in the uncontrolled environment of the patient's home than in the controlled and carefully monitored setting of the PACU, where use of postoperative opioids has been routine. Second, data from trial C803-025, Cohort 2 indicate that nearly all laparoscopic cholecystectomy patients receive at least 1 dose of opioid rescue medication in the PACU, which would render both these endpoints effectively moot.

### 8.2.3 Modified Post-Anesthesia Discharge Scoring System (mPADSS)

PACU discharge eligibility will be assessed with the mPADSS, starting at 30 minutes after arrival in the PACU and repeated at 15 minute intervals ( $\pm 5$  minutes) until the patient is eligible for discharge (i.e. an mPADSS score of 9 or greater). The results will be recorded on the appropriate source document and eCRF. NOTE: patients must be monitored for vital signs for at least 2 hours after surgery as described in [Section 9.2.4](#), even if their mPADSS score indicates that they may be discharged. Conversely, patients must continue to be monitored and may not be discharged until the mPADSS score has reached 9 or greater. The time of arrival (b) (7) (C) (b) (7) (C) from PACU will also be recorded on the appropriate source document and eCRF.

mPADSS is a widely recognized, published tool used to determine eligibility for discharge from the PACU after ambulatory surgery ([Chung, 1995](#); [Awad and Chung, 2006](#)). The mPADSS includes an assessment of five parameters: vital signs, activity level, nausea/vomiting, pain, and surgical bleeding. For pharmacoeconomic purposes, this trial will evaluate eligibility for PACU discharge using a version of mPADSS that has been slightly modified for ease of administration and to suit the surgical model under study (b) (7) (C). The mPADSS tool provides a standardized means of assessing eligibility for PACU discharge across multiple investigative

sites and also ensures that nonmedical complications, such as a missing ride home, do not interfere with evaluation of test drug effects.

## 9.0 Assessment of Safety

### 9.1 Safety Assessments: Patient Visits and Follow-Up Phone Calls

- Adverse events
  - Spontaneously reported AEs; either volunteered by the patient, prompted by non-directed questioning or reported by an investigator will be documented on the eCRF.
  - The following AEs will be solicited and recorded at specified time points (see [Table 2](#)) using the Log Pad: dizziness, somnolence, constipation, nausea, vomiting, pruritus, headache, dysgeusia, hypoesthesia, and paresthesia
- Standard 12-lead ECG
- Safety Laboratory Tests (Serum chemistry, hematology, urinalysis)
- Vital Signs and Physical Examination
- Surgical site examination for CCI bruising, bleeding or drainage from the incision(s), hematoma, dehiscence, infection and healing

### 9.2 Method and Timing of Assessments

#### 9.2.1 Adverse Event Recording

**Pain that has been evaluated as part of the efficacy endpoints will not be considered an adverse event.**

Adverse events will be recorded from the time the patient signs the informed consent form through trial completion final visit/early termination (see [Section 9.3](#)).

##### 9.2.1.1 Spontaneously Reported Adverse Events

At each contact between the investigative site and the patient (visit or phone call), after the patient has had an opportunity to spontaneously mention any problems, the Investigator should inquire about the occurrence of AEs. All AE details including severity and causality from screening through trial completion will be recorded by trial staff on the appropriate source document and AE eCRF.

##### 9.2.1.2 Solicited Patient-Reported Adverse Events

The solicited patient-reported AEs that must be recorded at specified times on the LogPad (see [Table 2](#)) are: dizziness, somnolence (drowsiness), constipation, nausea, vomiting, pruritus

(itching), headache, Dysgeusia (metallic taste in mouth), paresthesia (tingling or pins and needles), and hypoesthesia (numbness) (see [Section 7.5](#)).

These ten adverse events were chosen for detailed study by solicitation on the LogPad for two reasons. First, many of these AEs are common symptoms associated with opioid administration ([Zhao et al, 2004](#); [Daniels et al, 2009](#); [YaDeau et al, 2011](#)). If treatment with SABER®-Bupivacaine results in a reduced consumption of rescue opioids compared to placebo or bupivacaine HCl, there may also be a concomitant reduction in the incidence of these adverse events. This reduction in opioid-related adverse events could then be regarded as an additional benefit of SABER®-Bupivacaine treatment.

CCI

If the patient reports an AE on the LogPad investigative site personnel will receive an alert. At each point of contact, investigative site personnel will follow-up with the patient regarding severity, frequency, duration and action taken of any AEs reported on the LogPad and appropriately document this data and causality in the source and AE eCRF.

### **9.2.2 12-Lead ECGs**

Standard resting 12-lead ECGs will be obtained at the Screening Visit, Visit 6, and Visit 7, or Early Termination Visit. Overall interpretation and machine read intervals (HR, PR, QRS, QT, and QTc) will be recorded on the ECG eCRF. Clinically significant ECG findings that emerge after treatment will be recorded on the AE eCRF.

### **9.2.3 Laboratory Tests**

All routine laboratory analyses will be conducted by a central laboratory and have been listed below. Laboratory tests will be obtained as indicated on the Schedule of Events table. Instructions on sample collection, processing and shipment will be provided in a separate laboratory manual.

Female patients of childbearing potential will have a serum pregnancy test at Screening and a urine pregnancy test on the day of surgery. The urine pregnancy test will be performed locally at the investigative site.

**Table 4: Safety Laboratory Tests**

Blood Chemistry	
ALT (SGPT)	Creatine Kinase (CK)
Albumin	Glucose
Amylase (screening only)	Lactate dehydrogenase (LDH)
AST (SGOT)	Lipase (screening only)
Alkaline Phosphatase	Phosphorus
Bilirubin (direct and total)	Potassium
BUN	Protein (total)
Serum Creatinine	Sodium
Calcium	Triglycerides
Cholesterol (total)	Uric Acid
Chloride	Bicarbonate
Hematology	
Hematocrit	Red blood cell (RBC) count
Hemoglobin	Platelet count
White blood cell (WBC) count with differential (absolute count and percent of neutrophils, lymphocytes, monocytes, eosinophils, and basophils)	
Other	
Serum and Urine Pregnancy hCG	
Routine Urinalysis including Color, Appearance, Specific Gravity, pH, Protein, Glucose, Ketones, Bilirubin, Blood, Urobilinogen, Nitrite and Leukocyte Esterase	
Urine drug toxicology screen for opiates, oxycodone, cannabinoids, amphetamines, cocaine, and methadone (screening only)	

Laboratory values that are out of range for the Central lab will be identified and may be repeated at the Investigator's discretion and sent to the Central lab. The Investigator will classify laboratory values outside the normal range as either clinically significant or not clinically significant. Clinically significant laboratory values outside the normal range that emerge after treatment will be recorded on the AE eCRF. Clinically significant out of range laboratory values that emerge after treatment will be followed and treated (if appropriate) by the Investigator until they return to normal.

#### **9.2.4 Vital Signs**

Systolic/diastolic blood pressure, heart rate, respiratory rate, and temperature will be measured. Blood pressure and heart rate will be measured after the patient has been resting (supine or sitting) for 5 minutes. Pulse oxygen saturation will be continuously measured on Visit 2 pre- and post-surgery, and recorded at 15 minute intervals for a period of at least 2 hours after surgery. Measurements will be taken at the times specified in the Schedule of Events table and will be recorded on the appropriate source document and Vital Sign eCRF.

**9.2.5 Physical Examination**

A physical examination including height and weight will be conducted at the Screening Visit to confirm if the patient meets trial criteria.

A physical examination (including weight) will be conducted at Visit 6 (Study Day 29) and Visit 7 (Study Day 60), or Early Termination Visit. Any changes from baseline outside the normal range that emerge after treatment will be recorded on the AE eCRF.

**9.2.6 Surgical Site Examination and Assessment of Surgical Site AEs**

At each clinic visit, the wound evaluator (an investigator or other medically qualified investigative site personnel who will remain blinded to treatment assignment) will assess the surgical sites for the presence or absence of bruising, bleeding or drainage from incision(s), hematoma, dehiscence, or infection. CCI

[REDACTED]

[REDACTED]

[REDACTED]

[REDACTED]

[REDACTED]

[REDACTED]

CCI [REDACTED]

[REDACTED]

[REDACTED]

[REDACTED]

[REDACTED]

[REDACTED]

[REDACTED]

[REDACTED]

[REDACTED]

[REDACTED]

[REDACTED]

Surgical site healing will also be assessed with a questionnaire at the Study Day 2 and Study Day 3 Follow-up Phone Calls CCI [REDACTED]. This questionnaire may elicit clinically significant alterations in surgical site healing. During the next clinic visit (or earlier if medically necessary) investigative site personnel will follow-up on questionnaire responses suggesting clinically significant alterations in surgical site healing.

**9.3 Adverse Events**

**9.3.1 Definitions**

**Adverse Event**

An adverse event (AE) is any untoward medical occurrence in a patient or clinical investigation subject administered a pharmaceutical product and which does not necessarily have to have a causal relationship with this treatment. An AE can therefore be any unfavorable and unintended sign or symptom, including clinically significant laboratory values and test results, concomitant illness, accident, or worsening of an existing medical condition.

The following should not be recorded as an AE if noted at screening:

- A pre-planned procedure for an illness included in the patient's medical history, unless the condition for which the procedure was planned has worsened since baseline. Please observe that complications to pre-planned procedures should be recorded as AEs
- A pre-existing condition found as a result of screening procedures

Any worsening in severity or frequency of a baseline concomitant illness or any new illness diagnosed in the trial period must be regarded as an AE.

**Pain that is evaluated as part of the efficacy endpoints will not be considered an adverse event.**

### **Serious Adverse Event**

A serious adverse event (SAE) is any adverse event that, at any dose:

- Results in death
- Is life-threatening
  - Life-threatening refers to an event in which the patient is at risk of death at the time of the event. It does not include an event that, had it occurred in a more severe form, might have caused death
- Requires inpatient hospitalization or prolongation of existing hospitalization – Inpatient hospitalization includes an overnight admission
- Results in persistent or significant disability/incapacity
  - Disability is defined as a substantial disruption of a person's ability to conduct normal life functions
- Results in the birth of a child with a congenital anomaly/birth defect
- Important medical events that may not result in death, be life threatening, or require hospitalization may be considered an SAE (when based upon appropriate medical judgment). These events may jeopardize the patient and may require medical or surgical intervention to prevent one of the outcomes listed above

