### 5.3.2 Screening Exclusion Criteria

1. Pregnant or nursing females.
2. Patients with absolute or relative contraindications to laparoscopic cholecystectomy. These include, but are not limited to: generalized peritonitis, septic shock from cholangitis, severe acute pancreatitis, untreated coagulopathy, previous abdominal operations which prevent safe abdominal access or progression of the procedure, advanced cirrhosis with failure of hepatic function, and suspected gallbladder cancer ([SAGES Guidelines, 2010](#)).
3. Patients with prior midline abdominal surgery who are at risk for adhesions that may complicate laparoscopic cholecystectomy and/or accurate pain assessments.
4. Patients requiring emergency surgery or urgent surgery (fewer than 5 days between screening and surgery). Patients that require the preoperative placement of a cholecystostomy tube for the management of acute cholecystitis are also excluded.
5. Patients with a pre-planned overnight stay or pre-planned hospital admission.
6. Patients scheduled for single incision, mini trocars, natural orifice transluminal endoscopic surgery (NOTES), robotic laparoscopic procedures, or any procedure (other than cholangiograms and minimal adhesiolysis) in addition to laparoscopic cholecystectomy.
7. Patients with known hypersensitivity to amide local anesthetics such as bupivacaine.
8. Patients with acute pain that is not due to cholecystitis.
9. Patients with a history of chronic pain unrelated to gallbladder disease.
10. Patients with ongoing depression or psychosis.
11. Patients undergoing long-term treatment with opioids or other analgesics, including acetaminophen, NSAIDs, anticonvulsants (gabapentin or pregabalin), and antidepressants (SSRIs, SNRIs, and tricyclics), but not including daily low-dose aspirin (see full list of excluded medications in [Section 7.6.1](#)).
12. Patients who are being treated chronically with systemic corticosteroids or who will require peri-operative corticosteroids because of adrenal insufficiency (inhalational or topical corticosteroids are permitted).
13. Patients who may be unsuitable for opioid administration (such as sensitivity [e.g., history of severe nausea and vomiting] hypersensitivity, known history of abuse or addiction, or unwillingness to take prescribed rescue opioids).

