## 7.0 Trial Procedures

Surgery will be performed under general anesthesia as described in [Section 5.5](#) at a hospital or ambulatory surgical center. Discharge will occur on the day of surgery per local practice. If conversion to open surgery is necessary, or more than 4 ports have been deemed necessary during the trial, then the patient is **not** to be dosed with test drug.

Operating room (OR) personnel will be un-blinded due to inherent differences between SABER®-Bupivacaine and Placebo saline or bupivacaine HCl in viscosity and color. Assessment of study endpoints, adverse events and surgical site examinations, must be done by blinded personnel. Patients must remain blinded throughout the study. Investigators will be asked to sign a form for each patient that appropriate personnel have remained blinded to patient group assignment.

During the first 72 hours after test drug administration (i.e., through [REDACTED] Day 4/Postoperative Day [POD] 3) pain intensity, both [REDACTED] on movement (defined as sitting up, or attempting to do so, from a supine position), will be recorded by the subject using a 11-point (0-10) numerical pain rating scale (NPRS) on an electronic diary (LogPad®) at specified times after recovery from anesthesia (see Table 2: Patient LogPad Schedule of Events).

Pain intensity [REDACTED] on movement will also be recorded (1) prior to each IV fentanyl administration requested by the patient in the PACU, and (2) at home before the patient self-administers either rescue medication. [REDACTED]

[REDACTED] Patients should then record their pain-on-movement score by sitting up, or attempting to do so, from a supine position and recording the worst pain experienced during the sit up. If the patient is unable to sit up all the way due to severe pain, weakness, or lack of recovery from anesthesia, the patient should be instructed to make his or her best attempt, and that score will be recorded.

If a patient is admitted to the hospital following test drug administration, pain assessments and rescue medication should follow the same instructions as for home use, to the extent possible.

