#### **7.4.3 Follow-up Calls (Study Day 2 and 3)**

##### *Postoperative Day 1 and 2*

Blinded site personnel will complete the following evaluations during the follow-up calls:

- Review completeness of Log Pad assessments and reminder of importance of completion of all LogPad assessments in a timely manner.
- Review of Adverse Events (including details of any patient-reported AEs recorded on the LogPad) – All reported AEs will be documented as noted in [Section 9.3](#)
- Inquire about Surgical Site AEs – [CCI]
- Review of Rescue Analgesia and Concomitant Medications – All other reported concomitant medications must be documented as noted in [Section 7.6](#)
- Inquire about Level of Activity including ambulation, sleeping, and eating – [CCI]
- Medical Resource Utilization Assessment – including any hospital admissions, Emergency Department visits, or calls to their physician or surgeon with complaint of unmanageable pain, nausea/vomiting, or refills of rescue opioid prescription – [CCI]

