#### **11.9.1.3 Stopping due to Non-Fatal Serious Adverse Events**

The SAC will review all SAEs reported during the PERSIST trial. The SAC may un-blind the patient data relating to any SAE it wishes to examine in detail for the purpose of determining whether stopping criteria have been met. The study will be stopped upon the occurrence of three non-fatal SAEs (including any wound hematoma, dehiscence, pruritus, and bruising), each of which, in the judgment of the SAC, meets all of the following provisions (1), (2), and (3):

- (1) SABER-Bupivacaine was administered to the patient.
- (2) The SAE had a temporal relationship to administration of SABER-Bupivacaine
- (3) A clear alternate cause for the SAE is not readily apparent

If the SAC recommends that the trial not be stopped because the SAEs under review fail to meet the stopping criteria, it may instead recommend revisions to the study protocol to enhance patient safety and may also recommend a pause in enrollment until such revisions can be implemented.

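### As defined, an overnight admission solely for pain scored as an efficacy outcome is not an adverse event, so it is not recorded or reviewed as an SAE

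*Combined protocol and SAP*

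**What the plan says.** All references are to the combined protocol and SAP.

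- **The exclusion.** Section 9.3.1: "Pain that is evaluated as part of the efficacy endpoints will not be considered an adverse event". Section 9.2.1 has the same rule: "Pain that has been evaluated as part of the efficacy endpoints will not be considered an adverse event". Neither is qualified.
- **The SAE definition.** Section 9.3.1: "A serious adverse event (SAE) is any adverse event that, at any dose", followed by the seriousness criteria. One of these is hospitalization, with the note that "Inpatient hospitalization includes an overnight admission".
- **The setting.** Section 5.3.2 excludes "Patients with a pre-planned overnight stay or pre-planned hospital admission", so an overnight stay after surgery is unplanned. Sections 6.3 and 8.2.2 both foresee that some patients will be admitted.
- **Pain scoring in hospital.** Section 7.0 sets pain scoring over the first 72 hours and adds: "If a patient is admitted to the hospital following test drug administration, pain assessments and rescue medication should follow the same instructions". The sentence goes on to name the home-use instructions, and asks for this only as far as is feasible.
- **Where an admission is otherwise captured.** The Medical Resource Utilization assessment asks about hospital admissions, emergency visits and "calls to their physician or surgeon with complaint of unmanageable pain" (Section 7.4.3, with similar items at Visits 3 to 6 and at early termination).
- **What the SAC sees.** Section 11.9.1.3: "The SAC will review all SAEs reported during the PERSIST trial". Section 9.3.3 requires a report within 24 hours for SAEs.

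**The concern.** Pain is the efficacy outcome, and the exclusion lets that outcome decide which hospitalizations count as harm. Keeping ordinary post-operative pain scores out of the adverse event tables is sensible. Applying the same rule to pain bad enough to keep an outpatient in hospital overnight is another matter, because the protocol elsewhere treats that admission as serious.

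Two things are at stake. The first is completeness: an admission of this kind would be missing from the SAE tables and from the SAC's SAE review. The second is comparability. The trial tests whether the arms differ in pain. If they also differ in pain admissions, more admissions drop out of the SAE count of the arm that has more of them. In addition, up to 25 sites (Section 6.1) would each have to decide whether to apply the exclusion literally or report the admission anyway, which makes ascertainment uneven.

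**Working it through.** The plan states no figure on this point, so there is none to reproduce. The check is a reading of the definitions in sequence, followed by an illustration of size.

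**Tracing one case.** A patient has an unplanned overnight admission within 72 hours of dosing, and the only reason is pain that the patient is scoring on the diary.

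1. Is the pain an adverse event? No. It is evaluated for the efficacy endpoints (Sections 9.2.1 and 9.3.1). Admission does not change this, because scoring is meant to continue in hospital where feasible (Section 7.0).
2. Is it an SAE? The hospitalization criterion is met, but an SAE is defined as a kind of adverse event. Step 1 has already answered no.
3. Is it reported within 24 hours? That duty attaches to SAEs (Section 9.3.3). No.
4. Is it in the SAC's SAE review? That review covers reported SAEs (Section 11.9.1.3). No.
5. Does any visible sentence restore it? None was found. In the same Section 9.3.1, the rule on pre-planned procedures does carry an exception for worsening and a reminder to record complications. The pain rule carries neither.
6. Is the admission recorded at all? Yes, through the Medical Resource Utilization assessment. That assessment is not in the visible list of safety variables in Section 11.10.1, and no visible text reconciles it with the adverse event records.

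**Illustration of size.** Inputs: n = 132 per arm in Part 2 (Section 5.4). The rate p of overnight admission solely for efficacy-scored pain is not in the documents and is assumed here. Section 11.10.1 reports safety in three arms and pools SABER-Bupivacaine over both parts. Assuming that half of the approximately 90 Part 1 patients received it, that arm has 132 + 90/2 = 177.

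Expected number left out = n × p. Chance of at least one in an arm of 132 = 1 − (1 − p)^132.

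| Assumed p | 132 × p | 177 × p | Chance of at least one in 132 |
|---|---|---|---|
| 0.5% | 0.7 | 0.9 | 48% |
| 1% | 1.3 | 1.8 | 73% |
| 2% | 2.6 | 3.5 | 93% |
| 3% | 4.0 | 5.3 | 98% |
| 5% | 6.6 | 8.9 | 99.9% |

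**Between-arm effect, two arms of 132.** The SAE difference is distorted by 132 × (p₂ − p₁):

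- 1% against 1%: 132 × 0 = 0
- 1% against 2%: 132 × 0.01 = 1.3 patients
- 1% against 5%: 132 × 0.04 = 5.3 patients

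**The case against.** The case on the other side is that this is a narrow gap in wording, and that several stronger readings do not follow from the text. Most of that stands.

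- **A reader might infer that severe pain can never reach the SAC.** The exclusion covers only pain evaluated for efficacy, which in the visible text is scored through 72 hours. A hematoma, dehiscence or infection behind the pain, a co-occurring event such as vomiting, and later pain all remain reportable. Blinded staff examine the wound at each clinic visit (Section 9.2.6). The medical monitor may also convene the SAC over safety events generally, not only SAEs (Section 11.9.1.1). That route is discretionary, however, and creates no SAE record.
- **A reader might infer that the stopping rule is disabled.** Control-arm SAEs never count towards it (Section 11.9.1.1). A SABER-Bupivacaine SAE counts only if no other clear cause is apparent (Section 11.9.1.3), and recent surgery is an obvious candidate cause of post-operative pain. The effect on the rule is small.
- **A reader might infer that SAEs are under-counted in the arm with worse pain control.** The documents do not show this. It requires pain admissions to differ by arm, no rates are given, and both arms have the same rescue medication. Worse pain is also not hidden, since it is the primary endpoint.
- **A reader might infer that pain admissions would outnumber the SAEs of special interest**, each expected in under 1% (Section 9.3.4). An assumed rate that starts at 1% builds that result in. At 0.5% the expected count is 0.7 per arm.
- **Redaction.** Text after the Medical Resource Utilization items, one safety variable and parts of Section 9.2.6 are blacked out, and the full SAC Charter and Safety Monitoring Plan are not supplied. A rule there cannot be excluded.

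What the objection does not remove is the operative rule. It is visible in two places, it is unqualified, and it conflicts with the protocol's own treatment of an overnight admission as serious.

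**Conclusion.** The point holds in a limited form. Followed literally, the definitions keep an unplanned overnight admission solely for efficacy-scored pain, within the 72-hour window, out of the SAE records, the 24-hour report and the SAC's SAE review. This is a stated rule that yields a less complete safety count.

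The size is unknown because the documents give no admission rate; the figures above are illustrations under assumed rates. Bias between arms is conditional: the arm with more pain admissions would be under-counted, and the distortion of the rate difference is zero if the rates are equal. The conclusion assumes that sites apply the exclusion as written and that no redacted or unsupplied document overrides it. It is a change that should be made because it is cheap. It does not put the primary efficacy analysis in doubt.

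**What to change.** In Sections 9.2.1 and 9.3.1, replace the unqualified exclusion with wording to this effect: *pain recorded as an efficacy score is not an adverse event unless it meets a seriousness criterion, including overnight admission or readmission, in which case it is recorded as an AE and SAE.*

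Then, before unblinding, reconcile every hospital admission and emergency visit on the Medical Resource Utilization assessment against the AE and SAE records. Add a table of pain admissions by treatment arm to the safety summaries in Section 11.10.1, so that any imbalance can be seen however individual sites classified the events.

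The cost is one sentence in two sections, one check on data already collected and one table. The downside is a few more SAE reports: at an assumed 1% in both Part 2 arms, 264 × 0.01 = 2.6. Ordinary pain scores stay outside adverse event reporting, and patient care does not change.
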